The proposed study will use a randomized controlled clinical trial design. A sample of 60 black women who report at least weekly binge eating episodes will be randomized to 2 arms of a 6-month AAT + BWL intervention: AAT+BWL or a control group. AAT+BWL participants will receive an 8-week AAT program, and an 8-week BWL program, both using a group format. Assessments will be conducted at 0, 4, and 6 months. This study will be conducted at one site: UNC Department of Family Medicine.

The goal of AAT is to enable participants to be able to relearn their stomach's hunger signals and begin to obey and monitor functions of satiety 11. AAT has been successful in helping participants diagnosed with Binge Eating Disorder (BED) and bulimia nervosa reduce binge eating, overeating, urges to eat in response to non-appetite stimuli, and prevent weight gain. 12-14 The AAT intervention includes eight 60-minute group sessions. All sessions involve didactic training, review of self-monitoring of eating episodes, interactive activities, and homework assignments to enable participants to practice learned skills. Participants will be provided a workbook, which will include session content, and self-monitoring forms.

The curriculum for BWL (behavioral weight loss) will be based on the evidenced-based curriculum from the Diabetes Prevention Program, or Prevent T2. Eight weekly session will review core content including healthy eating, increasing physical activity, and caloric balance. An outline of session curriculum is attached to the protocol.

[figure not shown]
Physical measures will be taken by trained staff, who will be supervised by [name], PI of this project. The following equipment will be used:

- 1. Height /Weight** will be measured on a digital scale and a wall-mounted stadiometer.
- 2. Waist Circumference** will be measured twice with a Gullick II measuring tape.
- 3. Blood pressure** assessment will be measured using an GE Dinamap Procure Auscultatory 400 Multi-Parameter Patient Monitor with the subject in a sitting position after at least a minute rest period.

Questionnaires:

- 1. Eating Disorder Examination (EDE-Q)** is a self-reported questionnaire based on the Eating Disorder Examination.
- 2. Beck Depression Inventory (BDI)24** is a 21-item questionnaire that measures symptoms and attitudes associated with depression.

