6.4. Consent Process

If participants are eligible for the study, the applicant will be given a date and time to meet with the PI and will be provided an email link to access the self-report measures associated with this study. At appointment, participants will provide signed informed consent, finish self-report measures, and be evaluated in person to determine the presence of at least one weekly binge eating episode using the overeating section of the Eating Disorder Examination. Participants will also have their height, weight, blood pressure, and waist circumference measured at this time. Baseline appointment will take place in a private room at the UNC Department of Family Medicine. If all inclusion criteria are met, participants will be randomly assigned to one of the two treatment conditions. There will be a brief waiting period between the initial consent discussion and obtaining consent for this study. In addition, consent will be obtained by research assistants affiliated with this study, other than the study PI.

7. Study Intervention

[An interventional study may involve a drug, device, biologic agent, or a medical, surgical, dental, radiological, nutritional, neurological, or behavioral intervention. The study may use an experimental design (e.g. a randomized trial) or it may use an observational design (e.g., a single-arm study or study in which the physician and patient choose from among available treatment regimens). **Complete only the sections below that are relevant to your study; enter N/A otherwise.**]

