8.3. Enrollment / Baseline (Day 0)

If participants are eligible for the study, the applicant will be given a date and time to meet with the PI and will be provided an email link to access the self-report measures associated with this study. At appointment, participants will provide signed informed consent, finish self-report measures, and be evaluated in person to determine the presence of at least one weekly binge eating episode using the overeating section of the Eating Disorder Examination. Participants will also have their height, weight, blood pressure, and waist circumference measured at this time. Baseline appointment will take place in a private room at the UNC Department of Family Medicine. If all inclusion criteria are met, participants will be randomly assigned to one of the two treatment conditions.

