11.2. Assessment of Safety

To minimize emotional distress, if participants cite this concern, they will be provided the option to a) pause

and regroup; and/or b) finish the survey at a later time. If the previous is not sufficient, and participants report experiencing significant distress, participants will be provided the number to Hopeline (<https://www.hopeline-nc.org>; [contact]), a North Carolina crisis line and to the local emergency room.

Participants who experience significant distress will also be asked permission to provide their contact information to the PI ([name]). [name], who is a licensed clinical social worker, will contact those

participants on the next day. [name] will also be updated immediately on all participants who experience

significant distress.

Depression – Beck Depression Inventory

Using the total score (from all added scores on the BDI), the following interpretation applies:

Total Score	Range of Depression
0 – 13	Minimal
14 – 19	Mild
20 – 28	Moderate
29 – 63	Severe

Potential participants who on initial assessment (or is there a screening assessment) have a BDI-II score of 29 or greater (“severe” depression) are excluded from the study (please see below).

If a participant’s total score is 20 or greater, this will be reported to the Principal Investigator (PI) or Project Director (PD) who will discuss their results, inquire about current status and

treatment, will **provide information on community resources for the treatment of depression, and document the conversation and actions taken.**

For question #9 “Suicidal Thoughts or Wishes”: If a participant chooses response option 1, 2 or 3, this will be reported to the PI or PD who will discuss the results, inquire about current status and treatment and document the conversation and actions taken (providing a detailed note of the discussion that will be maintained using the participant’s ID number). The participant will also be referred to their PCP, given a list of mental health providers in the community, and urged to seek treatment if they are not already receiving treatment.

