If a participant endorses suicidality or imminent fear of self-harm, the PD will contact and inform the PI (who is a licensed mental health professional), and also make telephone contact with the local suicide crisis network while in the presence of the participant; if a significant other is with the participant, that individual will be provided with instructions to accompany the person to the nearest Emergency Room. In either of these situations, the individual will be asked for permission to contact and inform their PCP of their condition.

11.3.Unanticipated Problems, Adverse Events, Serious Adverse Events

Unanticipated Problems: An unanticipated problem is any incident, experience or outcome that meets all three OHRP criteria (1) unexpected (in severity, specificity, frequency, or nature), (2) related or possibly related to the research, and (3) suggests the research places subjects or others at greater risk than previously known or recognized.

Adverse Event (AE) Definitions: An adverse event is one that occurs during the course of a research protocol that either causes physical or psychological harm, or increases the risk of physical or psychological harm, or results in a loss of privacy and/or confidentiality to a research participant or others (such as family members).

Serious Adverse Events (SAE) Definition: A serious adverse event means any event temporally associated with the subject's participation in research that meets any of the following criteria: results in death; is life threatening (places the subject at immediate risk of death from the event it occurred); requires inpatient hospitalization or prolongation of existing hospitalization; results in a persistent or significant disability/incapacity; results in a congenital anomaly/birth defect; or any other adverse event that, based upon appropriate medical judgement, may jeopardize the subject's health and may require medical or surgical intervention to prevent one of the outcomes listed .

Reporting and Documentation Procedures:

Data and safety monitoring will be conducted during meetings with the PI and research assistants during which recruitment, data acquisition, management and any adverse events arising from the study will be reviewed. Any unanticipated and adverse events will be reported immediately to the IRB, a serious event will be reported to the IRB and funding agency.

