12.1.1.2. Consent Procedures and Documentation

Informed consent is a process that is initiated prior to the individual's agreeing to participate in the study and continues throughout the individual's study participation. Consent forms will be Institutional Review Board (IRB)-approved and the participant will be asked to read and review the document. The investigator will explain the research study to the participant and answer any questions that may arise. A verbal explanation will be provided in terms suited to the participant's comprehension of the purposes, procedures, and potential risks of the study and of their rights as research participants. Participants will have the opportunity to carefully review the written consent form and ask questions prior to signing. The participants should have the opportunity to discuss the study with their family or surrogates or think about it prior to agreeing to participate. The participant will sign the informed consent document prior to any procedures being done specifically for the study. Participants must be informed that participation is voluntary and that they may withdraw from the study at any time, without prejudice. A copy of the informed consent document will be given to the participants for their records. The informed consent process will be conducted and documented in the source document (including the

date), and the form signed, before the participant undergoes any study-specific procedures. The rights and welfare of the participants will be protected by emphasizing to them that the quality of their medical care will not be adversely affected if they decline to participate in this study.

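### Section 11.2 sets no time for reading BDI item 9, yet its crisis-network call is written only for a woman who is with staff

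*Combined protocol and SAP*

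**What the plan says.** Section 11.2 has three separate responses.

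- **Item 9.** "If a participant chooses response option 1, 2 or 3, this will be reported to the PI or PD who will discuss the results". That person also asks about current status and treatment and documents the conversation. The woman is referred to her primary care provider, given a list of local providers and urged to seek treatment. No time is set for reading, reporting or contact.
- **Suicidality or imminent fear of self-harm.** The project director informs the principal investigator and is to "make telephone contact with the local suicide crisis network while in the presence of the participant".
- **Significant distress.** The woman receives a crisis-line number and is directed to the emergency room. With her permission, the principal investigator contacts her the next day. The principal investigator "will also be updated immediately on all participants who experience" significant distress. A distressed woman may also complete the survey later; the place is not stated.

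The BDI, which Section 5 says "is a 21-item questionnaire that measures symptoms and attitudes associated with depression", is scheduled at baseline, 4 months and 6 months (Sections 5.3 and 8.1).

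On baseline access, Sections 6.4 and 8.3 say that an eligible woman receives an appointment and "will be provided an email link to access the self-report measures associated with this study". Section 8.3 continues: "At appointment, participants will provide signed informed consent, finish self-report measures, and be evaluated in person". Section 6.4 adds: "There will be a brief waiting period between the initial consent discussion and obtaining consent for this study". Section 12.1.1.2 requires consent to be documented "and the form signed, before the participant undergoes any study-specific procedures".

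**The concern.** The crisis call works only if the answer that prompts it is seen while the woman and a staff member are together. The plan does not require that. An item 9 answer could be read after she has gone home, or before she arrives if she used the emailed link. In either case the call cannot be made as written, and no alternative is given.

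What is at stake is participant safety, not the estimand or the analysis. The protocol itself expects some distressed applicants: Section 2.1 links binge eating disorder with mood disorders, and Section 11.2 provides for excluding women with severe BDI scores.

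**Working it through.** There is no figure in the plan to reproduce. The check sets the provisions side by side.

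**1. Is there a time limit for item 9?** Not in Section 11.2. Its two timed steps (immediate update, next-day contact) start from significant distress, not from an item 9 answer. A woman can mark item 9 without telling anyone that she is distressed. The exclusion at a BDI-II score of 29 or more implies that baseline forms are scored before randomization, but this does not place the reading of item 9 before she leaves.

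**2. Which steps need her to be present?**

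| Step in Section 11.2 | Starts from | Time stated | Needs presence |
|---|---|---|---|
| Discussion, referral to primary care, provider list | Item 9 answer of 1, 2 or 3 | None | No; can be done by telephone |
| Crisis-line number, emergency room direction | Significant distress | None | No |
| Update of the principal investigator | Significant distress | Immediately | No |
| Contact by the principal investigator | Significant distress, with permission | Next day | No |
| Call to the crisis network | Suicidality or imminent fear of self-harm | None | Yes, as written |

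The gap is therefore specific. If a telephone discussion of item 9 shows that a woman is in danger, the next written step assumes that she is in the room.

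**3. Could item 9 be answered away from staff?** Two things leave this open: the emailed link at baseline, and the option to complete the survey later at an unstated place. The link's contents are not listed. Because the BDI is a baseline questionnaire and the link is to the study's self-report measures, it may be included. No provision says that the link stays closed until consent is signed. Equally, none says that measures are completed before the visit.

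**4. Does the gap depend on the link?** No.

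- *BDI completed on site after consent:* she is present when she answers, but nothing makes staff look at item 9 before she goes.
- *BDI completed through the link:* she is absent when she answers, and the answer may be unread until her visit.

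The first case is milder, but in both the call may be impossible when the answer is read.

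**5. Size.** The documents give 48 or 60 randomized women. With 3 BDI time points and no dropout, that is 3 × 48 = 144 to 3 × 60 = 180 planned item 9 answers, besides baseline answers from women not randomized. The link is documented at 1 of the 3 time points. If Section 8.3 is followed for everyone, at least 48 or 60 women receive it. The numbers recruited for screening (160 in Section 6.1, 200 in the synopsis) are only a loose ceiling, because the link goes to eligible women. Neither the share completing measures early nor the frequency of non-zero item 9 answers is given.

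**The case against.** A reader might infer that the plan collects the BDI off site and before consent. The documents do not support that. The BDI's presence on the link and its completion before the visit are both inferences, and both would have to hold. Section 12.1.1.2 forbids study procedures before the form is signed. Sections 5, 6.3, 6.4 and 8.3 all list consent before the self-report measures. Sections 5 and 6.3 speak of finishing those measures without mentioning a link, so the word need not mean that they were started at home. Supplying a link does not itself breach the consent rule; only using it early would.

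A reader might also infer that staff have no written way to reach a woman who is elsewhere. That is too strong as well, since the item 9 discussion and the referral can be done by telephone.

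No link is documented at months 4 and 6, where Sections 8.6 and 8.7 list the BDI with physical measurements. Part of Section 12 before the safety officer paragraph is not in the text available for review, and that paragraph refers to a reporting frequency given above it, so some reporting timing may stand there.

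All of this stands and narrows the point. It does not supply a reading time for item 9 in Section 11.2 or a form of the crisis call for a woman who is not present.

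**Conclusion.** The point holds in a limited form. Section 11.2 sets no time for reading item 9, and its crisis-network call can be carried out as written only with the woman present. Under either reading of the baseline procedure, an answer may be read when she is not there. The emailed link and the option to complete the survey later make this more likely, but off-site or pre-consent BDI completion remains a possibility, not a stated plan.

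The timing gap covers all 3 BDI time points; the link bears on baseline only. The size of the risk cannot be estimated from the documents. The conclusion assumes that the unavailable part of Section 12 contains no item 9 timing rule. This is an inexpensive safety improvement, and it does not call the trial's design or analysis into question.

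**What to change.** 1. **Baseline:** have the BDI completed on site after signed consent. Either leave it off the emailed link or state that the link opens only after consent.
2. **Every BDI time point:** have a named staff role read item 9 before the woman leaves, so that the item 9 discussion and, if needed, the crisis call can take place while she is there.
3. **If any remote completion is kept**, including a survey completed later after distress: require same-day review of item 9 and add a telephone version of the crisis step for a woman who is not present.

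The cost is a few sentences in Sections 6.4, 8.3 and 11.2 and a few minutes of existing staff time per visit. The sample size, assessment schedule and analysis do not change.

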- 3. Weight Efficacy Life-Style Questionnaire (WEL) 25:** The WEL is a 20-item questionnaire that assesses participants' level of confidence in resisting eating in varied situations and in different emotional states, with higher scores indicating more confidence.
- 4. Eating Disorder Examination – Overeating Section (EDE) 20** is a semi-structured interview to assess symptoms and DSM-IV diagnoses for Bulimia Nervosa, Anorexia Nervosa, and BED. Eating disorder symptoms are assessed on four subscales: restraint, eating concern, shape concern, and weight concern. The EDE has well-established validity, reliability, and has been used extensively as an established measure of disordered eating behavior.
- 5. Modified Sociodemographic Questionnaire** will be used to collect: age, marital status, education, neighborhood residence, employment status, household size, religious background, and income. Randomization will be performed by Microsoft Excel and the PI will be blinded to all randomization. A research assistant will be responsible for supervising randomization. Prior to randomization, potential participants will respond to flyers and will be screened to determine eligibility. If an individual is eligible, she will be given a date and time to meet with a research team member. Participants will be evaluated in person or by phone to determine the presence of at least one weekly binge eating episode using the overeating section of the Eating Disorder Examination. Participants will also complete anthropometric measurements, provide signed informed consent, and finish self-report measures. Once all baseline assessments are complete, participants will be randomized to the AAT + BWL intervention or control group. Participants will be assessed at 0, 4 months, and 6 months. Data on the AAT group will be collected at 3 time points: baseline, before randomization (T1); end of month 4, after the completion of intervention program (T2); and end of month 6, posttreatment follow up (T3). Data on the control group will be collected at: baseline (T1), 4 months (T2), and at the end of 6 months (T3).

Example #1 Flow diagram (e.g., randomized controlled trial). Customize to your study flow.]

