5.1. Treatment Design

The proposed study will use a randomized clinical trial design. A sample of 48 Non-Latino, AA women (BMI ≥ 25 kg/m²; rationale: *prior clinical and research experience suggests that AA women within this BMI range are most likely to identify their eating as problematic and engage in a clinical intervention*²⁶) who report at least weekly binge eating episodes will be randomized to 2 arms of a 6-month intervention: **AAT + NUTR** or **wait-list control**. **AAT + NUTR** participants (n=24) will first receive a weekly, group-based AAT program for the first two months, and then will begin NUTR and receive weekly, group sessions for the next 2 months. **Wait-list control group** (n=24) participants will receive an abbreviated AAT treatment at the end of 6 months. Following the intervention, UNC WMP providers (e.g., social workers, preventive medicine residents), and participants will be asked to participate in a 30-60 minute interview on the acceptability of the AAT +NUTR program, and to explore factors that will increase dissemination and uptake in the primary care setting.

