8.1. Table of Events

Measure	Description	Assessment Schedule		
		Baseline	4 months	6 months
Eating Disorder Examination – Overeating Section (EDE) ³⁵	A semi-structured interview to assess symptoms and DSM-V diagnoses for Bulimia Nervosa, Anorexia Nervosa, and BED.	X	X	X
Modified Sociodemographic Questionnaire	A questionnaire to collect age, marital status, education, neighborhood residence, employment status, household size, religious background, and income	X		
Height /Weight	Will be measured on a digital scale and a portable stadiometer.	X	X	X
Eating Disorder Examination-Questionnaire (EDE-Q) ³⁶	A 41-item scale to assess disordered eating behaviors and attitudes.	X	X	X
Dietary Intake (e.g., overall energy intake, fat, fruit and vegetable intake)	Two-24-hr dietary recall interviews (telephone-based) will be conducted on randomly selected days during a 2-week period.	X		X
Beck Depression Inventory ³⁷	A 21-item instrument used for measuring attitudes and symptoms of depression.	X	X	X

[In the following sections 7.2 – 7.8, fully describe:

- All contact with subjects (study visits, telephone/electronic contact)
- Permissible time windows for study procedures, lab tests, etc. While a treatment visit may have a small window (such as ± 1 day),

a 6-month follow-up call may have larger window (such as ± 1 week)

- Clearly distinguish activities and procedures that participants will complete in the course of clinical care from those that participants will complete solely for research purposes]

Study Activities	Year 01				Year 02			
	Q1	Q2	Q3	Q4	Q1	Q2	Q3	Q4
Aim 1: Feasibility Study								
Start-up								
Recruitment								
Conduct of feasibility study								
Data Analysis								
Presentations and publications								
Aim 2: Acceptability Interviews								
Semi-structured interviews and analysis								
Presentations and publications								
Prepare and submit R-series grant								

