8.4. Study Visits (Numbered as V1, V2, etc., Day X ± Y)

Participants will attend 8 weekly AAT sessions and then transition to eight, weekly NUTR sessions. All sessions will be 60-90 minutes.

V1: Data on AAT group and control group collected at baseline, before randomization (T1)

V2: Data on AAT group and control group collected at end of month 4, after completion of intervention program (T2)

V3: Data on AAT group and control group collected data end of month 6, posttreatment follow-up (T3)

Data collected includes height, weight, blood pressure, and waist circumference.

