8.7. Follow-Up Contact (Day Day X ± Y)

[Describe information/data to be collected, e.g., adverse events, disease progression/recurrence.]

<Insert text>

Data collected at end of month 6, posttreatment follow up, includes: height, weight, blood pressure, and waist circumference. Participants will also be asked to complete the Eating Disorder Examination, Eating Disorder Examination-Questionnaire, Weight Efficacy Lifestyle Questionnaire, and the Beck Depression Inventory.

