11.1. Risk / Benefit Assessment

Potential Risks:

The major risks are likely to be fatigue, distress from revealing personal information and possibly during the intervention trial if the participant is not feeling like she is making progress. If participants complain about fatigue or distress, they will be given an opportunity to complete the questionnaire later.

Potential Benefits: [State anticipated direct benefit(s) for individual subjects, if any, or to society]

Participants may benefit from the tools learned within the intervention, and healthy non-eating coping skills. Study participants will also have the opportunity to receive support from sharing of their experiences and may receive further insight regarding tools to manage their binge eating behaviors and gain awareness for future weight loss attempts. They may also experience pride in knowing that they are contributing to a study that may make a significant contribution to the field in the future.

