Participant Notification of New Information: All participants will be aware of new safety information within 7 days of the event preceding the development of new information.

11.4.Safety Monitoring

Data and safety monitoring will be conducted during meetings with the PI and research assistants during which recruitment, data acquisition, management and any adverse events arising from the study will be reviewed. Any unanticipated and adverse events will be reported immediately to the IRB, a serious event will be reported to the IRB and funding agency.

11.5.Study Suspension / Early Termination of the Study

Given that this is such a minimal risk intervention, we do not expect that serious AEs will occur and require stopping the trial. Though extremely unlikely, difficulties with compliance and/or attrition would be far more likely to result in trial stoppage. However, as previously noted, we, along with our safety officer, will closely monitor any injury rates and notify the UNC Chapel Hill IRB and the UNC NORC if a larger than expected SAE rate is observed.

12. Supporting Documentation and Operational Considerations

12.1.Regulatory, Ethical, and Study Oversight Considerations

The following subsections should include a description of the regulatory and ethical considerations, and context for the conduct of the trial. Of note, the guiding ethical principles being followed by this study are included in the **Statement of Compliance** at the beginning of this protocol. For NIH Intramural Research Program studies only: A statement referencing compliance with NIH Human Research

Protections Program policies and procedures is adequate for **Subsection 10.1.1, Informed Consent Process.**

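### No scheduled contact asks about injury, hospitalisation or other non-psychological harm, so these events would be known mainly if volunteered, and the treated arm has 16 more scheduled contacts at which to volunteer them

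*Combined protocol and SAP*

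**What the plan says.** Section 11.5 (Study Suspension / Early Termination) says that the team and its safety officer will follow injury rates and will "notify the UNC Chapel Hill IRB and the UNC NORC if a larger than expected SAE rate is observed". Section 11.3 defines adverse events broadly, covering physical and psychological harm and loss of privacy. Sections 11.3 and 11.4 have events reviewed at staff meetings and reported to the IRB.

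The data collection sections are narrower:

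- The schedules in 5.3 and 8.1 have no adverse-event row.
- Section 8.4 says of the three assessments: "Data collected includes height, weight, blood pressure, and waist circumference". Sections 8.6 and 8.7 add the EDE, EDE-Q, WEL and BDI and nothing on harms. The template prompt in 8.7 reads "Describe information/data to be collected, e.g., adverse events, disease progression/recurrence", and the text entered beneath it does not take up adverse events.
- Section 8.5 (Phone Contact) is an unfilled placeholder.
- Section 8.8 asks women who discontinue for the EDE-Q only.
- Section 9.3 (Outcome Measures for Evaluation of Safety) is N/A.

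Contact differs by arm. For the treated arm, 8.4 states: "Participants will attend 8 weekly AAT sessions and then transition to eight, weekly NUTR sessions". Both arms are assessed at months 4 and 6. The shared schedule also marks dietary intake at month 6: "Two-24-hr dietary recall interviews (telephone-based) will be conducted on randomly selected days during a 2-week period". Under 5.1, wait-list "participants will receive an abbreviated AAT treatment at the end of 6 months", which is also when the last assessment falls. Section 11.1 names distress as a risk, "possibly during the intervention trial if the participant is not feeling like she is making progress".

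**The concern.** The plan relies on event rates that its own visit plan does not collect. Without a question put to every woman, an injury or hospital stay is recorded only if she mentions it or it comes to light in some other way. Treated women meet study clinicians weekly for 16 weeks, and those clinicians are supervised weekly by the PI. Controls have no scheduled contact between baseline and month 4. With the same true risk in both arms, more events would probably be recorded in the treated arm, and the total seen by the safety officer would undercount controls.

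The trial is meant to lead to a larger study (10.6). Harms data gathered this way would be hard to interpret for that purpose, whether read by arm or pooled.

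A second, separate matter is that wait-list women receive abbreviated AAT when no further BDI, weight or other assessment is scheduled.

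**Working it through.** The plan gives no expected SAE rate, threshold or contact count in the available text, so it has no figure of its own to reproduce here. The check is a count of contacts followed by an illustration on stated assumptions.

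**1. Scheduled contacts per woman after randomization**

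- Treated, sessions and assessment visits: 8 AAT + 8 NUTR + 2 assessments = 18. Control: 2.
- Adding the two month 6 recall calls (5.3, 8.1) in each arm: 18 + 2 = 20 and 2 + 2 = 4.
- The gap is 16 either way (18 − 2 = 20 − 4 = 16). The acceptability interviews (15 to 20 people) are not counted.

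**2. Illustration of differential detection**

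Assumptions, none of which the documents give:

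- The event time is uniform over 26 weeks, with equal true risk in both arms.
- Sessions fall at weeks 1 to 16, assessments at weeks 17.33 and 26, and recall calls at weeks 25 and 25.5.
- Attendance is full.
- Each contact after the event elicits it with probability q, the same for every type of contact.

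If k(t) is the number of contacts after an event at week t, then capture = average over t of 1 − (1 − q)^k(t).

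Worked case, q = 0.1, 18 v 2 contacts:

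- Control: two contacts remain for events up to week 17.33 and one after that. Capture = [17.33 × (1 − 0.9²) + 8.67 × 0.1] / 26 = (3.293 + 0.867) / 26 = 0.16.
- Treated: in weeks 1 to 16 the remaining contacts fall from 18 to 3, then to 2, then to 1. The sum of 1 − 0.9^k for k = 3 to 18 is 10.061. Capture = (10.061 + 1.33 × 0.19 + 8.67 × 0.1) / 26 = 11.181 / 26 = 0.43.
- Ratio = 0.430 / 0.160 = 2.7.

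| q | 18 v 2: treated, control | ratio | 20 v 4: treated, control | ratio |
|---|---|---|---|---|
| 0.1 | 0.43, 0.16 | 2.7 | 0.53, 0.31 | 1.7 |
| 0.2 | 0.60, 0.31 | 2.0 | 0.74, 0.55 | 1.35 |
| 0.3 | 0.70, 0.44 | 1.6 | 0.84, 0.72 | 1.2 |
| 0.5 | 0.81, 0.67 | 1.2 | 0.94, 0.91 | 1.04 |

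Outside this range, q = 0.05 gives 3.3 (18 v 2) and 2.0 (20 v 4), and q = 0.9 gives about 1.0 on both counts.

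**3. The same model with a scripted question at months 4 and 6**

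Assume that the question finds a past event with probability 0.9. If only scripted answers count, both arms have the same two opportunities: capture = [17.33 × (1 − 0.1²) + 8.67 × 0.9] / 26 = (17.157 + 7.803) / 26 = 0.96 in each arm, a ratio of 1. If volunteered events are added to the scripted ones, capture at q = 0.1 (18 v 2) is 0.967 against 0.965, and the ratio rounds to 1.0 at every q tried.

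**4. Women treated after the last assessment**

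With 24 per arm (Aim 1, 5.1) this is up to 24 of 48. With 60 evenly allocated (10.6) it is up to 30 of 60. Both are upper limits, because they assume that every control stays and takes up the offer.

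**The case against.** The other side has several good arguments, and much of what they say stands.

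- **The most prominent named risk is screened actively.** Distress features prominently in 11.1. Under 11.2 a BDI total of 20 or more, or any positive response to item 9, goes to the PI or project director, who follows it up and documents it. The BDI is scheduled at months 4 and 6 in both arms. This stands, and it takes depression and suicidality out of the point. It does not cover injury or hospitalisation.
- **No comparison of harms is planned.** Section 9.3 is N/A and the Aim 2 analysis contains none. A reader might infer that every arm comparison of harms would be biased. The documents do not support that: BDI, EDE, EDE-Q and weight follow one schedule in both arms, and hospitalisations or deaths probably depend less on contact frequency. The exposure is limited to volunteered events.
- **Safeguards exist case by case.** Sections 11.3 and 11.4 send adverse events to the IRB and serious ones also to the funder, which needs no rate. Reasons for drop-out are documented (9.1, 10.1). A reader might infer that the 11.5 trigger cannot work. That goes too far, because serious events can still surface and 11.5 says none is expected. Part of the safety oversight text (12.6 to 12.7) was also not available for review. The surviving part refers back to a reporting frequency and mentions a stopping rule, so a threshold may be stated there.
- **The size rests on assumptions.** The reporting probability has no source in the documents, and leaving out the recall calls makes the imbalance look larger. Both counts are therefore shown, with a range.
- **The wait-list gap is a different matter.** It follows the month 6 endpoint and cannot bias the 0 to 6 month comparison. The distress and reporting procedures in 11.2 and 11.3 are also not limited to month 6.

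None of this supplies a question on physical harm at any scheduled contact. That omission rests on Sections 5.3, 8 and 9, which were available.

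**Conclusion.** The point holds in a limited form. In the available text no scheduled visit or discontinuation contact asks about injury, hospitalisation or other non-psychological harm, although 11.5 relies on monitoring injury and SAE rates. Such events would be known mainly if volunteered, and treated women have 16 more scheduled contacts.

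For an assumed reporting probability of 0.1 to 0.5 per contact, equal true risks would show as a ratio of about 1.0 to 1.7 on the fuller count of contacts, or 1.2 to 2.7 on sessions and assessment visits alone. These figures illustrate direction and plausible size. They assume full attendance and the same chance of disclosure at every type of contact, and they are not estimates for this trial. The distortion largely disappears if nearly every event is volunteered.

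The late start of AAT in the wait-list arm (up to 24 of 48 or 30 of 60 women) is a gap in safety follow-up only. Overall this is a cheap improvement worth making. It does not affect the efficacy analysis.

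**What to change.** - Add the same short scripted questions to the month 4 and month 6 assessments in both arms: injury, hospitalisation and any other harm since the last assessment, with the date.
- In 9.3 replace N/A with descriptive counts, by arm, of women with adverse events and serious adverse events, taken from those questions. No test is needed with 24 to 30 women per arm.
- Tabulate events volunteered at sessions separately, and keep them out of the by-arm counts.
- Give the same form once to wait-list women after their last abbreviated AAT session.
- Reconcile the wording in 11.5 on an SAE rate above expectation with the safety oversight text in 12.6 to 12.7, so that a reader can see what the rate is compared with.

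The cost is a few minutes at two existing assessments, one extra short form for wait-list women and some data entry. More events will probably be reported, which should be foreseen when the counts are read.
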